6.4 CONCOMITANT MEDICATION AND SUPPORTIVE CARE GUIDELINES

Supportive measures for optimal medical care are to be given throughout the study as indicated by the treating physician's assessment of the participant's medical need and institutional and general medical guidelines for the care of participants undergoing treatment of AML.

Medications required to treat AEs, manage cancer symptoms, concurrent diseases and supportive care agents, such as pain medications, anti-emetics and anti-diarrheals are allowed in general. The participant must be told to notify the investigational site about any new medications begun after the start of the study treatment. All medications (other than investigational products) and significant non-drug therapies (including vitamins, herbal medications, physical therapy and blood transfusions) administered during the study must be listed on the CRF.

6.4.1 BLOOD PRODUCTS

All blood products are to be irradiated and leukocyte-reduced according to institution guidelines. Additionally, cytomegalovirus (CMV)-negative participants should receive CMV-negative blood products according to institution guidelines.

Medications that inhibit Platelet Function and Anticoagulants: Caution should be exercised if patients are required to take medications that inhibit platelet function or anticoagulants. Participants enrolled in this study should not take concomitant medications which durably inhibit platelet function unless medically necessary and caution should be used if anticoagulation is required. For such medications, a wash-out period of 7 days is required prior to starting kinase inhibitor therapy. Agents that inhibit platelet function transiently or inhibit coagulation by other mechanisms are restricted; however, if anticoagulation is required while on study this must first be reviewed with the pharmacist and the study PI.

Medications that directly and durably inhibit platelet function include: Aspirin or aspirin-containing combinations, clopidogrel, dipyridamole, tirofiban, epoprostenol, eptifibatide, cilostazol, abciximab, ticlopidine.

Medications that directly and durably inhibit anticoagulation include: Warfarin, heparin/low molecular weight heparin [e.g., danaparoid, dalteparin, tinzaparin, enoxaparin] exceptions are low-dose warfarin for prophylaxis to prevent catheter thrombosis and heparin for flushes of IV lines.

6.4.2 INFECTION PROPHYLAXIS

The use of prophylactic antibacterial, antifungal, and antiviral agents is recommended according

to institutional guidelines.

Note, certain antibiotics may have interactions with specific inhibitors and thus this must be reviewed closely prior to study enrollment and while on study.

Possible prophylaxis includes use of prophylaxis for HSV infection with acyclovir or valacyclovir; levofloxacin for bacterial prophylaxis, as long as patient is not febrile.

The azole isavuconazole can likely be used concurrently with the study drug without dose adjustments. However if other azoles are prescribed such as posaconazole, fluconazole, or voriconazole, caution must be used as prophylaxis and may require measurement of drug levels to monitor dose. Potential interaction of antifungals should be reviewed with an oncology pharmacist and the study PI.

6.4.3 TREATMENT OF FEVER AND NEUTROPENIA

Neutropenic fever (defined as ANC <0.500/mm³ or 1.000/mm³ and known to be falling and temperature ≥38.0°C) will be treated per institution guidelines.

6.4.4 CYTOCHROME (CYP) INHIBITION

“JNJ-40346527 is a reversible inhibitor of primarily CYP3A4 and CYP2C8 and to a lesser extent of several other CYP isoforms (i.e., CYPs 2B6, 2C9, 2C19, and 2D6) in vitro. JNJ-40346527 increased the plasma exposure of midazolam (by ~65%) in a clinical Phase 1 study, suggesting a weak inhibition of CYP3A4 at clinically relevant doses. The clinical impact of co-administration of JNJ-40346527 with known inhibitors and inducers of CYP3A4/5, CYP2C8, or CYP2C19 are not fully understood. An increase or decrease of the systemic exposures of JNJ-40346527 and its active metabolites has to be anticipated.”^a

“Drugs that induce CYP3A4 activity may decrease JNJ-40346527 plasma concentrations. For participant in which CYP3A4 inducers are indicated, alternative agents with less enzyme induction potential should be used (Refer to Appendix B for detailed list of agents).

JNJ-40346527 is a substrate of CYP450 and is primarily metabolized through oxidative biotransformation catalyzed by CYP3A4 leading to the formation of carboxy metabolites. Minor pathways are catalyzed by CYP2C8 and CYP2C9 leading to monooxygenated metabolites. Concomitant use of JNJ-40346527 and drugs that inhibit CYP3A4 may increase exposure to certain kinase inhibitors. Caution is warranted when administering JNJ-40346527 to participants taking drugs that are highly dependent on CYP3A4 for metabolism and have a narrow therapeutic index. Systemic exposures to these medications could be increased while receiving JNJ-40346527.

Additionally, strong to moderate CYP3A4 inhibitors (e.g. ketoconazole, itraconazole, erythromycin, clarithromycin, atazanavir, indinavir, nefazodone, neflunavir, ritonavir, saquinavir, telithromycin) may significantly increase concentrations of JNJ-40346527 and should be used with caution when administered concurrently with JNJ-40346527.”^a

6.4.5 P-GLYCOPROTEINS (P-GP)

“JNJ-40346527 is an inhibitor of P-gp mediated transport of digoxin in vitro but was not a substrate for P-gp in vitro. Care should be taken if JNJ-40346527 is to be administered with P-

gp substrates" especially those with narrow therapeutic index (e.g., digoxin) and consultation with oncology pharmacist and Investigator is required (Refer to Appendix B for detailed list of agents).

6.4.6 GASTROINTESTINAL

Anti-emetics, anti-diarrheal agents and acid suppressive therapies should not be taken 2 hours before or after study drug (e.g., antacids, H2 blockers, and proton pump inhibitors) will be prescribed per institutional guidelines.

Study participants may receive anti-emetic therapy as needed during their treatment which may include ondansetron, prochlorperazine, haloperidol and lorazepam.

The use of anti-diarrheals will be administered per investigator's discretion. First line agents such as loperamide and tincture of opium, and/or octreotide can be utilized.

Nonclinical data demonstrates that JNJ-40346527 was not affected by the concomitant intake of medications inducing a pronounced and long-lasting reduction of gastric acid production such as proton-pump inhibitors or histamine H2 receptor antagonists. The use of acid reducing agents will be per investigators discretion.

6.5 PRECAUTIONARY MEDICATIONS, TREATMENTS, AND PROCEDURES

6.5.1 GENERAL PRECAUTIONS

JNJ-40346527 is an investigational drug. All subjects receiving JNJ-40346527 should be closely monitored according to the relevant clinical study protocol. While there has not been increased incidence of infection-related AEs observed, investigators should be vigilant for serious infections since JNJ-40346527 may impact subject's ability to fight infection via a reduction in macrophage function.

6.5.2 ANTIGENICITY AND MUTAGENICITY

There is no information on the risk of antibody formation against JNJ-40346527. JNJ-40346527 is not considered genotoxic based on the currently available in vitro and in vivo data.

6.5.3 IMPAIRMENT OF FERTILITY AND PREGNANCY

Since no fertility studies have been performed to date; it is possible that JNJ-40346527 may elicit embryofetal toxicity. JNJ-40346527 can only be administered in female and male subjects who practice effective birth control methods (refer to Appendix C) for 120 days after their last dose. For males no sperm donation should be allowed either during the study or within 120 days after last dose.

6.5.4 USE IN RENAL/HEPATIC DYSFUNCTION/FAILURE

Clinical studies in subjects with renal/hepatic impairment have not been performed to date; therefore, those subjects should be excluded from participation in studies of JNJ-40346527.

6.5.5 OVERDOSAGE AND ABUSE POTENTIAL

Information regarding overdosage and abuse of JNJ-40346527 is not available to date. General

supportive measures should be taken as appropriate.

6.5.6 CONTRAINDICATIONS

There are no contraindications identified at this time for JNJ-40346527.

6.6 PROHIBITED MEDICATIONS, TREATMENTS, AND PROCEDURES

No AML-directed concomitant therapy or investigational therapy is allowed during the study. Use of alternative medications (herbal or botanical for anticancer purposes) is not permitted during the study.

7. STUDY PROCEDURES/EVALUATIONS AND SCHEDULE

7.1 STUDY SPECIFIC PROCEDURES

7.1.1 MEDICAL HISTORY

A medical history will be obtained by the investigator or qualified designee. In addition to collecting information on demographics, the medical history will include all active conditions, and any prior conditions that are considered to be clinically significant by the PI. Details regarding the participant's AML will be recorded separately and not listed as medical history.

7.1.2 DISEASE ASSESSMENT

The investigator or qualified designee will obtain prior and current details regarding the participant's AML.

7.1.3 MEDICATION HISTORY

A complete medication history will be acquired concurrent with medical history.

7.1.4 PHYSICAL EXAMINATION

Physical exams must be performed by a medically qualified individual such as a licensed physician, Physician's Assistant or advanced Registered Nurse Practitioner as local law permits. The physical exam at baseline should include a complete physical exam per institutional standards. All other physical exams after baseline will include an evaluation of any AEs, or any previously reported symptoms, or prior physical examination findings.

As part of screening/baseline visit, physical examination is to be conducted within 14 days prior to start of treatment. All physical examinations will also include:

7.1.4.1 Vital signs

Vitals to be collected include BP, HR, and temperature. As part of screening/baseline visit, vitals should be obtained within 10 days prior to first dose of study agent. Vitals will also be obtained during treatment.

Significant findings that were present prior to the signature of the informed consent must be included in the Medical History eCRF page. Significant new findings that begin or worsen after informed consent must be recorded on the Adverse Event eCRF page.

7.1.4.2 Height and weight

Height is only required as part of screening.

7.1.4.3 Performance status

Performance status will be determined for all participants at screening and at select times during treatment as per assessment schedule in Section 7.10. Refer to Appendix B for performance criteria.

7.1.5 ELECTROCARDIOGRAM (ECG)

A standard of care ECG will be performed within 28 days prior to initiating treatment. Refer to schedule in Section 7.10.

7.1.6 MEDICAL DIARY

Participants that self-administer JNJ-40346527 are required to maintain a medical diary to assess compliance. Participants will receive instruction on how to administer JNJ-40346527 from a physician, clinical research nurse, or other designated, qualified healthcare provider. Participants will be provided with a medical diary and are required to record the date, dose, and the time of each oral dose.

7.1.7 ADVERSE EVENTS

Toxicities and adverse experiences will be assessed at each visit using the [CTCAE v5.0](#). Safety will be monitored by assessing physical examination, vital signs, body weight, performance status, as well as hematology, and chemistry as indicated in Section 7.10.

7.2 LABORATORY PROCEDURES AND EVALUATIONS

7.2.1 HEMATOLOGY

Hematologic profiling will be collected per institutional standards, and may include evaluation of hematocrit, hemoglobin, platelets, white blood cells with differential (basophils, eosinophils, lymphocytes, monocytes, neutrophils), and absolute lymphocyte count.

7.2.2 COAGULATION PANEL

INR, prothrombin time, and PTT.

7.2.3 BIOCHEMISTRY

Blood chemistry will be collected per institutional standards and may include the following: Creatinine, BUN, total bilirubin, Alkaline Phosphatase, serum electrolytes, magnesium, calcium, and potassium, phosphorous, as well as lactate dehydrogenase and uric acid. Testing for HCV B or C will only take place during screening

7.2.4 URINALYSIS

Glucose, protein, hemoglobin (blood), bilirubin, ketones, pH, and specific gravity. A microscopic exam should be performed for 2+ (~0.5 to 1.5 g/24 hours) or higher hemoglobin or protein levels.

7.2.5 BONE MARROW EXAM

Bone marrow aspirate must be collected at the visits outlined in the Section 7.10, Schedule of Events (Cycle 1 Day 29, Cycle 2 Day 29, Cycle 3 Day 29, and every 3 months following Cycle 3 Day 29. Additional bone marrow evaluations may occur if clinically indicated at the discretion of

the investigator (e.g., at the time of suspected disease progression or disease remission.)

Bone Marrow Aspirate will be collected to assess:

- Hematopathology review
- myeloid:erythroid ratio per standard of care
- Cellularity (%)
- blast quantification per standard of care.
- Cytogenetics will be performed as standard of care.
- Pharmacokinetic assay described in Section 7.3.1. (5-8ml in sodium heparin)
- Flow cytometry: as standard of care per institutional standards and exploratory analysis described in Section 7.3.2.

7.2.6 SKIN PUNCH BIOPSY

Data analysis from next generation sequencing can be greatly simplified by comparison of a patient's tumor sequence with germline sequence. The comparison facilitates identification of mutations that are unique to the tumor and not inherited sequence polymorphisms. The currently recognized method for obtaining germline sequence (espoused by The Cancer Genome Atlas project) is through the sequencing of DNA from skin fibroblasts that are obtained from a 3.5mm skin punch biopsy. Skin biopsies will be collected during the standard of care bone marrow procedure once during the study. The skin punch biopsy can be collected at any bone marrow collection time point. This procedure replaces the normal skin incision made to access the bone and does not require any additional sterilization or anesthetic.

Briefly, the procedure will be performed with a skin punch. The skin biopsy will be placed in saline or on moist gauze and transported to the research lab. One half of the biopsy will be used for genomic DNA extraction using standard tissue extraction protocols/kits. The remaining half will be snap-frozen and stored at -80°C.

7.2.7 BLOOD COLLECTION

Blood will be collected at time points outlined in the Section 7.10, Schedule of Events .

Peripheral Blood (2.0 mL in EDTA tube) will be collected for hematologic profiling.

Peripheral Blood (10ml) collected in sodium heparin-coated tubes or sodium citrate tubes will be used for evaluation of serum biochemistry and coagulation, respectively.

Peripheral Blood (10-40 ml) collected in EDTA coated tubes will be used for genetic studies described in Section 7.3.3 and 7.3.4.

7.2.8 PREGNANCY TEST

A serum (β -HCG) or urine pregnancy test is required during screening for all persons of childbearing potential within 14 days of initiating study drug. If the urine pregnancy test is positive, a serum pregnancy test must be performed per institutional standards. Pregnancy tests (serum and/or urine tests) should be repeated, if required, per institutional guidelines.

7.3 BIOMARKER, CORRELATIVE, AND SPECIAL STUDIES

The two overarching aims of the proposed exploratory studies are to: (i) evaluate the pharmacokinetics of JNJ-40346527 and effective inhibition of CSF-1R in marrow aspirates using plasma inhibitory assays with established CSF-1R-sensitive cell lines, and (ii) identify the effect of JNJ-40346527 on leukemia cells and the immune microenvironment.

7.3.1 EVALUATE THE PHARMACOKINETICS OF JNJ-40346527 AND EFFECTIVE INHIBITION OF CSF-1R

Plasma inhibitory assays using GDM-1 cells (very sensitive to CSF-1R inhibitors) will be performed with bone marrow aspirates before treatment (no later than 14 days prior to start of treatment) and after 28 days to estimate the effective CSF-1R inhibition by JNJ-40346527 in plasma derived from the marrow. The goal is to evaluate how well JNJ-40346527 inhibits CSF-1R within the marrow microenvironment.

7.3.2 IDENTIFY AND QUANTIFY THE SPECIFIC SUBPOPULATION OF CELLS THAT EXPRESS CSF-1R IN SUBJECTS AND CORRELATE WITH CLINICAL RESPONSE TO JNJ-40346527.

Bone marrow aspirates or peripheral blood will be collected from subjects and analyzed for *ex vivo* sensitivity to JNJ-40346527 prior to entry. The samples will also be analyzed for CSF-1R expression using FACS analysis using the CLIA-certified clinical flow lab at OHSU. In addition to CSF-1R expression, the samples will be analyzed for standard immunophenotypic markers to identify the subpopulation that most highly expresses CSF-1R.

Preliminary data suggests that CSF-1R is expressed on a subset of CD14+ cells (a monocytic marker). This data supports our hypothesis that CSF-1R inhibition is not directly affecting the leukemia cells, but rather is targeting a smaller supportive cell population, as shown in **Figure 4**. Evaluation of pure CD14+ populations in AML samples is somewhat limited since a subset of AML samples express CD14+ on blasts; however, there is still a trend towards sensitivity to CSF-1R inhibition in samples that have higher expression of CSF-1R on non-leukemic CD14+ cells.

CSF-1R expression will be correlated with CD14 and standard immunophenotypic flow markers in the clinical flow lab (Table 5) to determine the specific population(s) that express CSF-1R and are likely to be a target of JNJ-40346527. CSF-1R expression in specific hematopoietic lineages will be correlated with *ex vivo* sensitivity to JNJ-40346527 and clinical response.

The goal of this aim is to identify the specific subpopulation of cells that expresses CSF-1R, and if a quantitative analysis of this population can be used to predict clinical response to CSF-1R inhibition.

Table 5. Clinical flow cytometry antibodies tested with CSF-1R in CLIA-certified lab.

CD1a	CD2	sCD3	cCD3	CD4	CD5	CD7	CD8
CD10	CD11b	CD13	CD14	CD15	CD16	CD19	CD20
CD22	CD33	CD34	CD38	CD45	CD56	CD58	CD64
TdT	CD103	CD23	CD25	CSF-1R			

An identical FACS analysis will also be performed on bone marrow biopsies after one month of therapy to assess the expression of CSF-1R and CD14+ cells after JNJ-40346527 treatment in

both clinical responders and non-responders. This will establish if there is a reduction only in the CSF-1R-expressing population, or if other lineages are also affected. For example, it may be that JNJ-40346527 only affects CD14⁺ cells that express CSF-1R, or JNJ-40346527 may shrink the entire population of CD14⁺ cells. The relative proportion of leukemia cells, B-cells, and T-cells will also be evaluated after treatment.

Since this work will be done in a CLIA-certified clinical lab using standard flow procedures and equipment, it would provide a companion diagnostic that could be rapidly incorporated into standard flow protocols for larger trials.

7.3.3 ASSESSING A GENETIC SIGNATURE THAT PREDICTS RESPONSE TO JNJ-40346527.

Genomic DNA from leukemia patients will be analyzed for frequent leukemia mutations to determine if there is a genetic signature that predicts response to JNJ-40346527. The GeneTrails [Hematologic Malignancies Gene Panel](#) developed at OHSU's [Knight Diagnostic Laboratory](#) covers 76 genes that are frequently mutated in both lymphoid and myeloid leukemia, and is run as a CLIA-approved (CLIA#38D2018256), standard-of-care test on leukemia patients (Refer to D). Additional sites will use their in-house leukemia panel per standard of care. Redacted source documentation from sites will be sent to OHSU for genetic marker analysis.

Sequencing data from participants who have clinically responded to JNJ-40346527 will be compared to that from non-responders, to determine if there are genetic markers of clinical response. The goal is to identify a potential genetic subtype of AML that predicts clinical response to JNJ-40346527, either alone or in combination with the quantitative and qualitative analysis of CSF-1R⁺ cells.

Additionally, coded and de-identified DNA samples will be stored in the [name] Lab (OHSU) for further retrospective analyses, including targeted sequencing, whole-exome sequencing, or methylation analysis. Samples will be stored indefinitely. Access to samples will be limited to study staff.

7.3.4 TRANSCRIPTOME ANALYSIS TO IDENTIFY POTENTIAL QUALITATIVE DIFFERENCES IN CSF-1R⁺ CELLS THAT PREDICT PATIENT RESPONSE.

RNAseq will also be performed on leukemia samples from expression signature in CSF-1R⁺ cells that predicts patient response. We hypothesize that there may be a qualitative difference in CSF-1R⁺ CD14⁺ and CSF-1R⁻ CD14⁺ cells that results in clinical sensitivity to CSF-1R inhibitors. This difference may not be detected by the CyTOF approach outlined above, as that requires using candidate phospho-protein and cytokines. RNAseq offers an unbiased way to analyze the functional difference between these cells.

CSF-1R⁺ CD14⁺ and CSF-1R⁻ CD14⁺ cells will be isolated with magnetic antibody sorting. Since not every subject will have sufficient cells for RNAseq, we will review the FACS analysis of patients at screening to identify subjects that are likely to have sufficient numbers of CD14⁺ and CSF-1R⁺ cells. Our preliminary data has found that CSF-1R⁺ cells account for about 1-3% of the total number of cells. 40 ml of peripheral blood will be collected from subjects with a total peripheral blood WBC>10. This WBC typically correlates with a yield of ~100 million cells after Ficoll separation, which will subsequently allow for collection of ≥ 1 million CSF-1R⁺ CD14⁺ cells to process for RNA. This peripheral blood sample will be collected on day 1 prior to JNJ-

40346527 treatment.

Collectively, these studies are aimed at identifying a genetic or expression signature of CSF-1R⁺ cells that predicts clinical response to JNJ-40346527, as well as uncovering potential mechanisms of resistance/adaptation.

7.3.5 MASS CYTOMETRY EVALUATION OF JNJ-40346527 EFFECT ON PHOSPHO-SIGNALING PROTEINS IN IMMUNE CELL POPULATIONS

This exploratory study will utilize mass cytometry (cytometry by Time of Flight, CyTOF) to evaluate the effect that JNJ-40346527 has on intracellular phospho-signaling of proteins within immune cell populations (i.e., cytotoxic T cells, etc.) in pre- and post-treatment samples. These studies are intended to identify biomarkers that predict patient response and prioritize potential combination strategies for future clinical trials.

Bone marrow aspirates and blood samples will be collected and purified by Ficoll gradient. The cells will be fixed and labeled with antibodies coupled to heavy metal isotopes for CyTOF using established protocols. Cells expressing CSF-1R will be evaluated by CyTOF to look at downstream signaling pathways such as phospho-STAT3/5, phospho-Akt, phospho-MAPK, phospho-p38 and phospho-S6. As a positive control, we will use the GDM-1 cell line, which has an activating mutation in CSF-1R and responds robustly to CSF-1R inhibition *in vitro*. Antibodies to identify relevant subpopulations of monocytes, lymphocytes, and leukemia cells will be used to analyze phospho-signaling in CSF-1R⁺ cells, CD14⁺ cells, and leukemia cells (Table 6).

[figure not shown]
Table 6. Antibody panel for analysis of kinase signaling and cytokine analysis by CyTOF.

CSF-1R	CD14	pSTAT3	pSTAT5	pMAPK	pS6	pP38	pAkt
EGF	FGF2	HGF	SDF1	VEGF	IL-6	IL-1 \square	MCP1
MCP2	CXCL1	IL-8	IL-10	RANTES	TGF \square	MIP1b	G-CSF
IL3	MIP1a	GCSF-1					

To examine the secreted proteins from the supportive cells, we will pretreat samples with a Golgi trap (brefeldin A) to retain secreted proteins in the cells for intracellular staining. A selection of signaling molecules known to impact leukemia cell survival will also be evaluated, including a focus on the CSF-1R⁺ and CD14⁺ cells. Particularly, we will investigate the expression of the ligand CSF-1, which may act in an autocrine manner to expand supportive CSF-1R⁺ cells ().

Bone marrow aspirates will be tested at screening and after one cycle of therapy to evaluate signaling in CSF-1R⁺ CD14⁺ cells, CSF-1R⁻ CD14⁺ cells, immune cell populations, and leukemia cells both before and after treatment. Responsive versus non-responsive subjects will be compared to determine if there is a qualitative difference in CSF-1R⁺ cells that predicts clinical response to JNJ-40346527, and if this population either disappears or is functionally altered by JNJ-40346527 treatment. The goal is to determine if there is a qualitative signature of CSF-1R⁺ cells that predicts clinical response to JNJ-40346527 that can be used to identify sensitive patients or immunotherapeutic targets in future clinical trials.

In addition to identifying a biomarker, we predict that CSF-1R inhibition will alter the leukemic immune microenvironment as well. This will be evaluated by CyTOF analysis pre- and post-treatment for each patient. Our CyTOF panels cover immune checkpoint proteins, B- and T-cell populations, NK populations, and leukemia surface antigens in addition to the microenvironmental proteins outlined (**Table 6**; **Error! Reference source not found.**). JNJ-40346527 may potentially increase expression of checkpoint proteins, alter specific immune populations such as NK cells, or increase expression of leukemia cell antigens that can be targeted with antibody-directed immunotherapies (CD123, CD33, etc.). **The goal is to identify promising combinations for future immunotherapy clinical trials.**

7.3.6 SCREENING EX VIVO SENSITIVITY TO SMALL MOLECULE INHIBITORS FOLLOWING CSF-1R INHIBITION.

Ex vivo sensitivity to a panel of small molecules will be performed on bone marrow samples pre- and post-treatment to determine how leukemia cells change in response to CSF-1R inhibition. Participants with an *ex vivo* IC₅₀ that is $\leq 20\%$ of the median IC₅₀ (to be determined with preclinical testing) will be considered sensitive to JNJ-40346527 (termed “assay positive”), whereas those with an IC₅₀ $> 20\%$ of the median IC₅₀ will be considered insensitive (termed “assay negative”).

The *ex vivo* drug screening platform contains ~175 small-molecules inhibitors, including numerous kinase inhibitors. Changes in sensitivity of bone marrow aspirates pre- and post-treatment (day 29) will be evaluated. Preliminary data suggests that CSF-1R inhibition affects secretion of paracrine survival signals from supportive cells in the microenvironment, which will lead to leukemia cell death. Removing paracrine survival signals may also reveal sensitivities to other small molecules that were previously obscured by paracrine survival signals. The goal of these studies is to identify novel drugs that could be used in combination, or sequentially, with JNJ-40346527.

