8.2 RESPONSE CRITERIA FOR AML

The objective response rate will be defined as \geq PR, including cytogenetic and molecular responses when applicable, and will be determined at the end of each cycle.

Complete Remission (CR)*:

- Bone marrow blasts < 5%;
- Absence of blasts with Auer rods;
- Absence of extramedullary disease;
- Absolute neutrophil count $>1 \times 10^9/L$ (1000/ μ L);
- Platelet count $> 100 \times 10^9/L$ (100,000/ μ L);
- Independence of red cell transfusions

Morphologic CR:

- Bone marrow blasts <5%;
- Absence of blasts with Auer rods;
- Absence of extramedullary disease;
- No hematologic recovery required

Partial Remission

- Relevant in the setting of phase 1 and 2 clinical trials only;
- All hematologic criteria of CR;
- Decrease of bone marrow blast percentage to 5% to 25%;
- Decrease of pretreatment bone marrow blast percentage by at least 50%

Cytogenetic Complete Remission (CRc):

- Reversion to a normal karyotype at the time of morphologic CR in cases with an abnormal karyotype at the time of diagnosis; based on the evaluation of 20 metaphase cells from bone marrow.

Molecular CR (CRm):

- Molecular studies are negative (i.e., normal molecular markers in persons with previously abnormal molecular studies (e.g. c-KIT, NPM1, FLT3).

CR with incomplete recovery (CRI): • All CR criteria except for residual neutropenia ($< 1 \times 10^9/L$ [$1000/\mu L$]), or thrombocytopenia ($< 100 \times 10^9/L$ [$100,000/\mu L$]).

Stable disease (SD) Not fulfilling either PR or PD criteria and clinical stability

Progressive disease (PD) Increase in blasts by $\geq 50\%$

Definitions of response criteria are amended from Cheson et al.²⁰

*All criteria need to be fulfilled; marrow evaluation should be based on a count of 200 nucleated cells in an aspirate with spicules; if ambiguous, consider repeat exam after 5 to 7 days; flow cytometric evaluation may help to distinguish between persistent leukemia and regenerating normal marrow; a marrow biopsy should be performed in cases of dry tap, or if no spicules are obtained; no minimum duration of response required.

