10.2.3 ANALYSIS OF THE EXPLORATORY ENDPOINT(S)

10.2.3.1 Transcriptome analysis to identify potential qualitative differences in CSF-1R⁺ cells that predict patient response

For statistical analysis, we will need >5 responders and non-responders. We anticipate this will be feasible with 14 participants enrolling on the assay positive arm (not all will respond *in vivo*, and the non-responders can be used for comparison). In addition, we will also collect samples from the 7 patients enrolling on the assay negative arm who are likely to be non-responders.

If sufficient participants initially respond to JNJ-40346527 but later develop resistance, we will also collect these resistant samples to be analyzed by RNAseq as a separate comparison group. This may provide insight into how patients develop resistance to JNJ-40346527.

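### The marker analyses rest on a responder versus non-responder contrast with about 4 responders per arm of 14; a co-reported rank analysis of marrow blast change would use data already collected

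*Combined protocol and SAP*

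**What the plan says.** Three correlative analyses define outcome as two groups.

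- Section 7.3.5 (mass cytometry): "Responsive versus non-responsive subjects will be compared to determine if there is a qualitative difference in" CSF-1R-positive cells.
- Section 7.3.3 (gene panel): "Sequencing data from participants who have clinically responded to JNJ-40346527 will be compared to that from non-responders".
- Sections 7.3.4 and 10.2.3.1 (RNAseq): "For statistical analysis, we will need >5 responders and non-responders". The plan adds "We anticipate this will be feasible with 14 participants enrolling on the assay positive arm", and that "we will also collect samples from the 7 patients enrolling on the assay negative arm who are likely to be non-responders".

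Section 7.3.2 (flow cytometry) is looser. It correlates CSF-1R expression with clinical response and asks "if a quantitative analysis of this population can be used to predict clinical response to CSF-1R" inhibition, without naming a test or a graded outcome. Its post-treatment part looks at responders and non-responders.

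The marrow examination in Section 7.2.5 includes "blast quantification per standard of care" on Day 29 of cycles 1, 2 and 3; footnote H of the Schedule of Events adds the screening marrow. In Section 8.2, partial remission requires "Decrease of pretreatment bone marrow blast percentage by at least 50" per cent, a blast level of 5 to 25%, and the hematologic criteria of complete remission.

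No section uses blast change as the outcome for a marker. Section 10.2.3 has an entry for RNAseq only, and no correlative analysis has a stated test, significance level or effect size.

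**The concern.** Section 1.6 makes finding biomarkers that correlate with clinical response the first goal of the correlative work. Response is in large part a cut of a graded measure. In a two-group comparison, a patient whose blasts fall by 45% counts the same as one whose blasts double. With few responders, most of the information about a marker lies in how the non-responders differ from one another, and the planned contrast discards it. These samples are meant to guide patient selection and combinations in later trials, so a weak contrast could miss a useful marker for which the data were in hand.

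**Working it through.** **1. The plan's own figure.** The Simon design has 7 patients in stage 1, continues with at least 1 response, and calls the treatment promising at 3 or more of 14. The probability of a promising result is Σ over i = 1 to 7 of P(X₁ = i) × P(X₂ ≥ 3 − i), with X₁ and X₂ binomial(7, p). At p = 0.05 this is 0.0274 and at p = 0.30 it is 0.810. The stated 5% level and 80% power reproduce. They apply to the primary endpoint and say nothing about the marker analyses.

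**2. Number of responders.** At 30%, 14 × 0.30 = 4.2. More than 5 means at least 6. P(X ≥ 6) for binomial(14, 0.30) = 0.126 + 0.062 + 0.023 + 0.007 + 0.001 + smaller terms = 0.22. Adding 7 assay-negative patients at an assumed 5% gives 4.2 + 0.35 = 4.55 expected and P(at least 6) = 0.29. Section 7.3.4 also accepts that some patients will have too few cells for RNAseq, so these are upper figures for that assay. With a single responder among 14, the smallest two-sided exact rank-sum p-value is 2/14 = 0.14.

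**3. Power if the relation is graded.** Assumptions not in the documents: marker x is standard normal, graded outcome y = ρx + √(1 − ρ²)e, a responder is a patient in the top 30% of y, and tests are two-sided at 5%, unadjusted. By simulation at n = 14:

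| ρ | Exact rank-sum on response | Spearman on y | Gain (points) |
|---|---|---|---|
| 0.4 | 14.7% | 26.2% | about 12 |
| 0.5 | 21.8% | 40.5% | about 19 |
| 0.6 | 32.4% | 58.0% | about 26 |
| 0.7 | 46.2% | 77.2% | about 31 |

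A separate set of runs gave 22/40%, 32/58% and 46/77% at ρ 0.5, 0.6 and 0.7, hence a range of 18 to 31 points. Fixing the count at exactly 4 of 14 gives 7 to 14 points at ρ 0.3 to 0.4 and 21.5 to 35.5 at ρ 0.5 to 0.7.

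**4. What shrinks or reverses the gain.**

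- Noise with reliability 0.8 in both outcomes: 19 v 33%, 26 v 47% and 37 v 63% at ρ 0.5, 0.6 and 0.7. With noise in blast change only, the gain is about 10 to 18 points (Pearson v t-test).
- Early loss with worst rank given to every lost patient, loss unrelated to the marker, ρ 0.5 to 0.7: about 4 to 7 points at 15% loss, and 0 to −4 points at 30%. If half the loss is unrelated: 11 to 18 and 6 to 12 points. If every lost patient would also have been lowest on the graded outcome, it stays near 17 to 30. The loss fractions are assumed.
- All-or-none relation, with the marker shifted only in responders: two-group 27%, 53% and 75% against rank analysis 20%, 36% and 49%, at shifts of 1, 1.5 and 2 SD.

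**The case against.** The strongest objection is that the protocol hypothesizes a qualitative difference in the supportive cells (Sections 7.3.4 and 7.3.5), and Section 1.2.1 says that these cells are not activated in every sample. That can be read as a threshold mechanism, for which the planned comparison is the better test. This stands, and it is why the rank analysis should not displace the planned one.

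Four further points also stand.

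- Blast change is not the clinical response that the objectives name: partial remission also needs count recovery and an absolute blast range.
- Peripheral blood may stand in for marrow at screening (Sections 3.1 and 7.4), so a marrow baseline is not assured.
- Table 6 lists 27 cytometry markers and the gene panel covers 76 genes. With Bonferroni over 27, Spearman power is only about 7 to 30% at ρ 0.5 to 0.7. Both analyses generate hypotheses.
- The simulation used a continuous marker, so it gives no figure for mutation status.

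A reader might infer that every correlative analysis is dichotomized. The documents do not support that: Section 7.3.2 is not strictly binary, and Sections 7.3.1 and 7.3.6 compare samples before and after treatment without using clinical outcome.

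A reader might also argue from the 5% rate that 0.95¹⁴ = 49% of arms of 14 would have no responder. The design rules this out, because an arm with 0 of 7 stops; at 5% that happens with probability 0.95⁷ = 0.70. With the stop applied, Spearman power at 5% is about 24 to 46%, not the 41 to 77% that a full 14 would suggest.

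**Conclusion.** The concern holds as a cheap improvement to exploratory analyses. The part that needs no assumption about the markers is the responder count: about 4 expected in an arm of 14 at the desired rate, and a 0.22 chance of meeting the plan's own need for RNAseq.

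The power gain is conditional. It is about 7 to 14 points at ρ 0.3 to 0.4 and 18 to 31 at ρ 0.5 to 0.7, for one continuous marker at n = 14 with a graded relation and no early loss. The documents give no ρ. It is tempting to say that the plan forfeits 18 to 31 points outright, or that blast change should become the main analysis. Neither follows: noise narrows the gain, marker-unrelated loss of up to 30% takes it to roughly zero, and an all-or-none relation reverses it. The primary endpoint and its design are unaffected.

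**What to change.** In Sections 7.3.2 to 7.3.5, with a matching entry in 10.2.3:

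- Keep the responder versus non-responder comparison.
- Pre-specify beside it, as a co-reported exploratory analysis, a rank analysis within each assay arm of best percent change in marrow blasts from the pre-treatment marrow through Cycle 3 Day 29. Use Spearman correlation for quantitative markers and a rank-sum test of blast change by mutation status for the gene panel.
- Restrict it to patients with a pre-treatment marrow baseline.
- Give the worst rank only to patients lost through death or disease progression before a post-treatment marrow, and show a sensitivity analysis without that rule.

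The cost is a few sentences and a few lines of code, with no new sample, visit or patient. The downsides are one more unadjusted exploratory result per marker, and an outcome that ignores the count-recovery part of response.
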